### **3.7 Safety Analyses**

Safety measures include: treatment exposure, adverse events, clinical safety lab, vital signs, physical examination, 12-Lead ECG, ECHO, concomitant medication use, and MRIs. Safety measures at Randomized Treatment Period and Randomized Treatment Period Post-Treatment Follow-up will be summarized in SAF1. Safety measures at OLE Period and OLE Post-Treatment Period will be summarized in SAF2.

Adverse events, lab shift table, and concomitant medication will be summarized by three analysis periods, including the Randomized Treatment Period using SAF1, Randomized Treatment Period Post-Treatment Follow-up among patients who do not continue to OLE using SAF1, and the combined OLE and OLE Period Post-Treatment Follow-up using SAF2. Start and end date of each analysis period is specified in the table below.

The rest safety measures will be summarized by nominal visit as collected in CRF, including vital sign, physical examination, clinical lab, Echocardiograph, ECG, and MRIs, etc.

Safety analysis period

	Period Start Date (inclusive)	Period End Date (inclusive)
Randomized Treatment Period (SAF1)	First dose date in Randomized Treatment Period	Volanesorsen group: Last dose date in the Randomized Treatment Period + one dose interval (7 days for weekly dosing schedule/ 14 days for bi-weekly dosing schedule) or first dose date in the OLE period -1 day, whichever is earlier.  Placebo group: if patient continue to OLE, end date will be first dose date of volanesorsen in the OLE period - 1 day. Otherwise, last dose date in the Randomized Treatment Period + one dose interval (7 days for weekly dosing schedule/ 14 days for bi-weekly dosing schedule)
Randomized Treatment Period Post-Treatment Follow-up (SAF1, patients who do not continue to OLE)	Last dose date in the Randomized Treatment Period + one dose interval (7 days for weekly dosing schedule/ 14 days for bi-weekly dosing schedule) + 1 day	End date of Post-Treatment Follow-up Period
Combined OLE and OLE Period Post-Treatment Follow-up (SAF2)	Volanesorsen group: Last dose date in the Randomized Treatment Period + one dosing interval (7 day for weekly dosing schedule/ 14 day for bi-weekly dosing schedule) + 1 day or first dose date in the OLE period, whichever is earlier  Placebo group: First dose date of volanesorsen in the OLE period	End date of Post-Treatment Period

If an AE starts in the Randomized Treatment Period and get worse in the combined OLE and OLE Period Post-Treatment Follow-up, the AE will be included in the summary of both period. If an AE starts in the Randomized Treatment Period and continues to the combined OLE and OLE Period Post-Treatment Follow-up in same or reduced severity, the AE will be included in the summary of first period only. If a concomitant medication starts in the Randomized Treatment Period and continues to

the combined OLE and OLE Period Post-Treatment Follow-up, the medication will be included in the summary of both periods

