**Table 4 Actions in Patients with Low Platelet Count or Drop in Platelet Count**  
*Continued*

Platelet Count on Rx	Drug Dose	Monitoring
100K/mm  - > 75K/mm 	Permanently reduce dose frequency to 300 mg every 2 weeks	
75K/mm  - > 50K/mm 	If occurs while on dose of 300 mg every 2 weeks then permanently discontinue Study Drug, otherwise dose pause When platelet count returns to > 100K/mm  restart dosing at dose frequency of 300 mg every 2 weeks only if approved by Sponsor Medical Monitor	Monitor every 2-3 days until 2 successive values are > 75K/mm  then monitor every 1 week Consider discontinuation of antiplatelet agents/NSAIDS/ anticoagulant medication
≤ 50K/mm 	
 
• Permanently discontinue Study Drug
 
	
 
• Monitor daily until 2 successive values show improvement then monitor every 2-3 days until 2 successive values are > 75K/mm^3 then monitor every 1 week
 
• Patient should be evaluated by a hematologist to provide diagnostic and therapeutic management
 
• Steroids recommended*. It is strongly recommended that, unless the patient has a medical contraindication to receiving glucocorticoids, the patient receives glucocorticoid therapy to reverse the platelet decline.
 
• Monitor triglyceride levels weekly and continue AE monitoring during steroid therapy
 
• Discontinue antiplatelet agents/NSAIDS/ anticoagulant medication while platelet count is < 50K/mm^3 if possible
 

\*\* Recovery in platelet count may be accelerated by administration of high dose corticosteroids. Treatment guidelines for immune thrombocytopenia ([Provan et al. 2010](#)) recommend dexamethasone 40 mg daily for 4 days every 2-4 wk for 1-4 cycles; prednisolone 0.5-2 mg/kg/day for 2-4 weeks then taper; or methylprednisolone 30 mg/kg/day for 7 days (**note:** may require continuation with oral corticosteroids after methylprednisolone)

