### **3.2 General Overview of Analyses**

#### **3.2.1 Statistical Methods**

All eCRF(Electronic Case Report Form) data, lab data transfers, as well as any outcomes derived from the data, will be provided in the patient data listings. Patient data listings will be presented for all patients randomized into the study. Descriptive summary statistics including n, mean, median, standard error, standard deviation, interquartile range (25th percentile, 75th percentile), range (minimum, maximum) for continuous variables, and counts and percentages for categorical variables will be used to summarize most data. Where appropriate, p-values will be reported. All statistical tests will be conducted using 2-sided tests with 5% Type 1 error rates unless otherwise stated.

Summary of primary efficacy endpoint will only include the on-treatment assessment. On-treatment assessment is defined as assessment since first dose date, up to 28 days after last dose of study medication. Assessment beyond last dose of study medication + 28 days will be excluded from efficacy summary. Lipid, hepatic fat fraction, and HbA1c assessments will be summarized by analysis visit according to the visit window defined in [Appendix B](#). Other assessments will be summarized by nominal visit as collected in CRF.

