### ***3.7.1 Imputation of Missing/Partial Dates***

#### ***3.7.1.1 Adverse Events***

For AEs, the following imputation rules will be applied to impute start dates under conservative principles:

- If year, month and day are all missing then assign the date of first dose of Study Drug
- If month and day are missing and year is:
  - the same as the year of the first dose of Study Drug then assign the month-day of first Study Drug
  - earlier than the year of the first dose of Study Drug then assign December 31
  - after the year of the first dose of Study Drug then assign January 1
- If only day is missing and month-year is:
  - the same as the month-year of the first dose of Study Drug then assign the day of first Study Drug
  - earlier than the month-year of the first dose of Study Drug then assign the last day of the month
  - after the month-year of the first dose of Study Drug then assign the first day of the month

Imputation will be performed only for the end date only if the day or month is missing (i.e., year is present) for a resolved AE as follows:

- If month and day are missing and year is
  - the same as the year of the last dose of Study Drug then assign the month-day of the last dose of Study Drug
  - otherwise, assign December 31
- If only day is missing then assign the last day of the month

If the imputed start date is later than the imputed end date then set the imputed start date to the imputed end date.

Analysis period will be assigned by comparing the imputed AE start date with the period start/end date.

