- TEAEs potentially related to Study Drug. Related is defined as “Related”, “Possible”, or missing relationship to Study Drug
- Any treatment-emergent adverse event by severity. At each level of patient summarization, a patient with multiple events is counted only once according to the worst reported severity. Adverse events with missing severity will be categorized as “Missing” for this summary.
- TEAEs potentially related to Study Drug by severity
- Serious TEAEs
- Serious TEAEs potentially related to Study Drug
- TEAEs leading to permanent treatment discontinuation
- TEAEs leading to death.

Adverse event summaries will be presented by descending frequency of the percentage of patients in the Total column. An overview of AEs will be provided for all TEAEs. Treatment-emergent AEs, treatment-emergent SAEs, TEAEs that lead to treatment discontinuation, and TEAEs leading to death will be listed. Note that imputed dates will be used for defining TEAEs and classification of TEAEs into analysis periods. Originally reported dates will be used for listings.

For AEs occurred during Randomized Treatment Post-Treatment Period, the frequency of patients and number of events of any TEAEs, Serious TEAE will be summarized by MedDRA preferred term and system organ class.

In addition, an overview of adjudicated AEs will be provided for pancreatitis and MACE separately. Adjudicated events will also be listed.

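### When a dose pause is never restarted, later platelet counts and adverse event records fall outside the randomised safety period, and no planned table joins treatment and follow-up by arm

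*SAP*

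**What the plan says.** - **Period end.** The safety analysis period table in SAP 3.7 gives one rule, in both arms, for patients who do not enter the OLE: the Randomized Treatment Period ends at "Last dose date in the Randomized Treatment Period + one dose interval (7 days for weekly dosing schedule/ 14 days for bi-weekly dosing schedule". The next day opens a separate analysis period, "Randomized Treatment Period Post-Treatment Follow-up among patients who do not continue to OLE using SAF1". SAF1 is the set of randomised patients who took at least one dose in the randomised period.
- **Placing adverse events.** SAP 3.7.1.1: "Analysis period will be assigned by comparing the imputed AE start date with the period start/end date".
- **Adverse event tables.** SAP 3.7.2 plans the full set (related, by severity, serious, leading to permanent discontinuation, leading to death) for the randomised period and the combined OLE period. For the randomised follow-up period it plans less: "the frequency of patients and number of events of any TEAEs, Serious TEAE will be summarized by MedDRA preferred term and system organ class".
- **Platelet tables.** SAP 3.7.4 tabulates the worst post-baseline platelet category in SAF1 and SAF2 by analysis period, and shift tables are also made for each period. SAP 3.2.1 admits unscheduled platelet results to these analyses.
- **Pauses.** Under Protocol 8.6.3 and Table 4, a count in the band from 75,000 down to just above 50,000/mm³ on weekly dosing leads to a pause with no fixed length. The monitoring instruction for that band is "Monitor every 2-3 days until 2 successive values are" above 75,000/mm³. Restart depends on recovery and on the Medical Monitor. The lowest band leads straight to permanent discontinuation.

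**The concern.** The period end depends only on the last dose taken. A pause is not known to be a permanent stop until later, and by then the period may already have closed, counted back from the last dose before the pause. Whether a pause-phase count belongs to the randomised period therefore depends on what happens afterwards. It belongs if dosing resumes, and it does not if dosing never resumes. The split follows the outcome of the pause.

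This matters because platelet decline is a known safety question for this drug. Protocol 2.3.4 reports a mild platelet decrease associated with the drug in Phase 2. It also reports that 6 of 182 patients in blinded ongoing trials had more pronounced falls with dosing interrupted or stopped, 2 of them below 25,000/mm³. A reader who takes the randomised-period platelet table as the full controlled comparison could see a milder worst category than the patient reached.

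**Working it through.** The point rests on a date rule, so the plan has no figure to reproduce. Take the last dose as Day 0.

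1. **Closure.** Randomised period = Day 0 to Day 7 (weekly) or Day 0 to Day 14 (every 2 weeks). Follow-up starts on Day 8 or Day 15.

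2. **The count that triggers the pause.** Protocol 8.5.3 requires a platelet result within 7 days before each dose. For a dose withheld on schedule, that sample is drawn on Days 0 to 7 (weekly) or Days 7 to 14 (every 2 weeks). All of these days lie inside the period. Only a delayed dose or a late retest puts the trigger outside.

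3. **Counts during the pause, weekly dosing.** Assume a triggering count on Day t and tests every 2 or 3 days up to Day 42. This is an upper bound on the number of tests, because Table 4 returns to weekly tests after recovery.

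| Trigger | Every 2 days: inside / total | Every 3 days: inside / total |
|---|---|---|
| Day 3 | 2 / 19 | 1 / 13 |
| Day 5 | 1 / 18 | 0 / 12 |
| Day 7 | 0 / 17 | 0 / 11 |

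4. **Follow-up after discontinuation.** Protocol 8.8.1 keeps patients who stop with a count below the lower limit of normal under the platelet rules for 6 weeks after stopping Study Drug. Counting those 42 days from the last dose, the share after closure is (42 − 7)/42 = 35/42 = 83% for weekly dosing and (42 − 14)/42 = 28/42 = 67% for every 2 weeks.

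5. **Dependence on the future (illustration; the days and counts are assumed).** Two weekly-dosed patients each have 60,000/mm³ on Day 6 and 55,000/mm³ on Day 12. One restarts on Day 28 on the every-2-weeks schedule, so the period ends no earlier than Day 28 + 14 = Day 42 and the Day 12 count is inside. The other never restarts, so the period ended on Day 7 and the Day 12 count is follow-up. If the Day 12 count were 40,000/mm³, Table 4 would stop treatment permanently. The randomised table would then show the 50,000 to <75,000 category and the follow-up table the 25,000 to <50,000 category.

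6. **Adverse event records.** Protocol 9.4.3.5 provides for a change in severity and for an event that becomes serious; in the latter case the onset date is new. SAP 3.7.2 counts a linked, worsened record as a separate treatment-emergent event. If that record starts after closure, it gets no severity, relatedness or leading-to-discontinuation table. SAP 3.7 says how to count an event that worsens in the OLE, but is silent on one that worsens in the randomised follow-up.

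7. **Weight of one patient.** With 20 per arm (the sample size section) to 30 per arm (up to 60 randomised 1:1), one patient is 1/20 = 5.0 to 1/30 = 3.3 percentage points. SAP 1.1 allows up to 70 patients, which would give 1/35 = 2.9.

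**The case against.** The strongest reply is that reporting treatment and follow-up separately is a legitimate choice, and that nothing is lost. Most of this stands.

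- **A reader might infer that the nadir disappears from the placebo-controlled tables.** The documents do not support that. The follow-up period is summarised in SAF1 for both arms, and worst platelet category and shifts are produced for it. Disposition (SAP 3.2.4) gives reasons for stopping by randomised group. Events leading to discontinuation are listed, and stopping-rule terminations get a listing with narratives. What is missing is one table that joins the two periods. The follow-up table covers only patients who skip the OLE, a subset defined after randomisation.
- **A reader might infer that the event that ended treatment drops out of the discontinuation table, at a cost of 3 to 5 points in the active arm.** Usually it does not. The triggering event normally starts inside the period (step 2). Protocol 9.4.3.3 offers no option for interrupted and not restarted, so that record would usually end as Permanently Discontinued and be counted. The loss arises only if a separate record starting after closure carries the flag.
- **A reader might infer that the worst cases are the ones displaced.** A count that meets the lowest band on schedule stops treatment directly and is itself inside the period, although a still lower later count could fall outside. Stops on every-2-weeks dosing have the 14-day window.
- **A reader might infer that the safety period should match the SAP's 28-day rule.** That rule, "On-treatment assessment is defined as assessment since first dose date, up to 28 days after last dose of study medication", governs the primary efficacy summary and is not a safety standard. Moving the safety end date to 28 days or to the recorded discontinuation date, whichever is later, would lengthen observation for paused patients and so create a different imbalance.

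**Conclusion.** The point holds as a gap in reporting. After a pause that is never restarted, platelet findings later than one dose interval after the last dose are split from the randomised-period tables according to how the pause ended. Adverse event records that start after closure receive a reduced set of tables. On weekly dosing nearly all pause-phase counts are affected (step 3).

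The number of patients affected cannot be derived. The documents give no time to platelet nadir, so a nadir after Day 7 (weekly) or Day 14 (every 2 weeks) is an assumption; an earlier nadir stays where it should. Each displaced patient would be 3.3 to 5.0 percentage points of an arm of 20 to 30. For the discontinuation table, that size applies only where a later, separate record carries the discontinuation. The documents do not support a claim that data are lost or that the discontinuing event is generally missing. The change is still worth making, because it is cheap and removes a split that depends on the outcome of the pause.

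**What to change.** Keep the period definitions in SAP 3.7. Add, for SAF1 by treatment arm, cumulative tables from first randomised dose to the end of randomised-period follow-up, cut off at the first OLE dose for patients who enter the OLE:

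- worst platelet category, with the platelet shift from Baseline;
- treatment-emergent events leading to permanent discontinuation, by severity and relatedness.

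Counting across both periods also covers an event that worsens during follow-up.

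The cost is a few extra tables from data already collected. Some unrelated late events will be counted, in both arms. No change to dosing, monitoring or stopping rules is involved.

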### ***3.7.1 Imputation of Missing/Partial Dates***

#### ***3.7.1.1 Adverse Events***

For AEs, the following imputation rules will be applied to impute start dates under conservative principles:

- If year, month and day are all missing then assign the date of first dose of Study Drug
- If month and day are missing and year is:
  - the same as the year of the first dose of Study Drug then assign the month-day of first Study Drug
  - earlier than the year of the first dose of Study Drug then assign December 31
  - after the year of the first dose of Study Drug then assign January 1
- If only day is missing and month-year is:
  - the same as the month-year of the first dose of Study Drug then assign the day of first Study Drug
  - earlier than the month-year of the first dose of Study Drug then assign the last day of the month
  - after the month-year of the first dose of Study Drug then assign the first day of the month

Imputation will be performed only for the end date only if the day or month is missing (i.e., year is present) for a resolved AE as follows:

- If month and day are missing and year is
  - the same as the year of the last dose of Study Drug then assign the month-day of the last dose of Study Drug
  - otherwise, assign December 31
- If only day is missing then assign the last day of the month

If the imputed start date is later than the imputed end date then set the imputed start date to the imputed end date.

Analysis period will be assigned by comparing the imputed AE start date with the period start/end date.

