#### ***3.7.1.2 Prior/Concomitant Medications***

For prior/concomitant medications, the following imputation rules will be applied to impute start dates under conservative principles:

- If year, month and day are all missing then assign the date of first dose of Study Drug

- If month and day are missing and year is:
  - earlier than the year of the first dose of Study Drug then assign December 31
  - otherwise, assign January 1
- If only day is missing and month-year is:
  - earlier than the month-year of the first dose of Study Drug then assign the first day of the month
  - otherwise, assign the last day of the month

Imputation will be performed only for the end date only if the day or month is missing (i.e., year is present) for a stopped prior/concomitant medication as follows:

- If month and day are missing then assign December 31
- If only day is missing then assign the last day of the month

If the imputed start date is later than the imputed end date then set the imputed start date to the imputed end date.

Analysis period will be assigned by comparing the imputed medication start/end date with the period start/end date.

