### **3.7.2.3 *Adverse Events of Special Interest:***

Treatment-emergent Bleeding, Hypersensitivity/Immunogenicity, Hepatotoxicity, Nephro-toxicity adverse events will be summarized using MedDRA preferred term and system organ class. Relationship between Treatment-emergent Bleeding event and presence of Concomitant Anti-Coagulant or Anti-Platelet Medication will be explored. Concomitant anti-coagulant or anti-platelet medications include medications that were taken before or on bleeding event onset date/time and stopped on or after bleeding onset date/time or ongoing at the end of study.

The Bleeding TEAE will be defined based on the Haemorrhages (SMQ) Export from MedDRA.

The Hypersensitivity/Immunogenicity TEAE is defined as AEs with either of two condition 1) meet Hypersensitivity (SMQ) Export from MedDRA, or 2) preferred term “Drug specific antibody” or “Drug specific antibody present” within system organ class “Investigations”.

The Hepatotoxicity TEAE will be defined based on the Drug-related hepatic disorders – comprehensive search (SMQ) Export from MedDRA, excluding neoplasms.

The Nephrotoxicity TEAE will be defined based on, either the Acute Renal Failure (SMQ) Export from MedDRA, or Proteinuria (SMQ) Export from MedDRA.

Treatment-emergent bleeding adverse events will be listed as well.

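### Partial AE start dates have no anchor at the first OLE dose, so placebo patients' day-missing events in the switch month are normally counted in the placebo period

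*SAP*

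**What the plan says.** SAP 3.7.1.1 states that its "imputation rules will be applied to impute start dates under conservative principles". For an AE start lacking only the day:

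- if the month-year is "the same as the month-year of the first dose of Study Drug then assign the day of first Study Drug", so an ambiguous event counts as on treatment;
- if it is "after the month-year of the first dose of Study Drug then assign the first day of the month".

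With month and day both missing, a year later than the first-dose year gives January 1. The start-date rule contains no branch for the first OLE dose.

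The imputed date then decides the table: "Analysis period will be assigned by comparing the imputed AE start date with the period start/end date". SAP 3.7.2 repeats this: "Note that imputed dates will be used for defining TEAEs and classification of TEAEs into analysis periods".

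The period table in SAP 3.7 ends the randomised period of a placebo patient as follows: "if patient continue to OLE, end date will be first dose date of volanesorsen in the OLE period - 1 day". The combined OLE period starts on that dose. SAP 3.7 also says that an AE starting in the randomised period and continuing at the same or lower severity is summarised in the first period only.

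For a medication start lacking only the day, SAP 3.7.1.2 assigns the first of the month if the month precedes the first-dose month; "otherwise, assign the last day of the month". A start imputed later than the stop date is reset to the stop date. In SAP 3.7.2.3, the anticoagulant or antiplatelet drugs considered with a bleed "include medications that were taken before or on bleeding event onset date/time" and were stopped on or after onset or are ongoing.

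**The concern.** A placebo patient has two treatment starts: placebo at Day 1 and volanesorsen at the first OLE dose. The AE rule resolves doubt towards exposure at the first and has nothing at the second. In the switch month, doubt is resolved towards placebo, so an event that may have followed first exposure to volanesorsen is reported under placebo. Unless it worsens, it is then absent from the OLE summary. SAP 3.7 uses explicit wording for the first OLE dose where it means that date, so the first dose of Study Drug in 3.7.1.1 cannot easily be read as covering it.

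The second, narrower matter is that a drug newly started on study with an unknown day is dated as late in the month as its stop date allows. This can break its link to a bleed earlier in that month, in an analysis meant to look for that link.

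**Working it through.** The plan gives no figure to reproduce. The check applies the date rules as written.

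**Inputs.** AE and medication rules: SAP 3.7.1.1 and 3.7.1.2. Period limits: SAP 3.7. Study Drug means active or placebo: protocol glossary. First OLE visit: Study Day 365 with a window of 2 days either side, protocol Appendix A (open label). Assumption: first-dose dates spread evenly over 2016 to 2019, for illustration only.

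1. **Which branch applies.** All first-dose dates in those four years with five possible switch days give 1,461 × 5 = 7,305 combinations. The switch falls in the same month-year as the first dose in 0 of them, so the first-of-month branch always applies.

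2. **Where the AE lands.** The imputed start precedes the switch in 7,065 of 7,305 cases (96.7%). The other 240 are switches on the 1st, which are classified as OLE.

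3. **How often that could be wrong.** In a month of n days with the switch on day k, n − k + 1 days are on or after the switch. Averaged over k, the share is (n + 1)/(2n); for n = 31 this is 32/62 = 51.6%. The enumeration also gives 51.6%. Of those days, the share placed in the placebo period is 1 − 2/(n + 1), because only k = 1 is classified correctly; for n = 31 this is 1 − 2/32 = 93.8%. The enumeration over all months gives 93.6%. The remaining 48.4% of days in the month are truly pre-switch and are placed correctly.

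4. **Worked case.** First dose 15 March 2017, switch 14 March 2018. An AE recorded as March 2018 becomes 1 March 2018 and goes to the placebo period.

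5. **Year-only AE starts.** Where the switch year is later than the first-dose year, January 1 precedes the switch in 7,257 of 7,277 cases (99.7%). The share of that year on or after the switch depends on the date: 292/365 = 80% for 15 March, 78/365 = 21% for 15 October.

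6. **Bleeding link.** Take a bleed on 5 March and an antiplatelet drug started on an unknown day that March, after the first-dose month. If the drug is ongoing, its start becomes 31 March. If it stopped on 10 March, the start is reset to 10 March. Both follow the bleed, so the drug is not linked. If the bleed also lacks a day, it becomes 1 March and an ongoing drug 31 March, so again there is no link.

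7. **Scale of one event.** One placebo patient is 1/20 = 5 percentage points with the 20 per arm of the sample-size section, or 1/35 = 2.9 points with 70 randomised 1:1 (SAP 1.1).

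**The case against.** Several points limit the concern, and most of them stand.

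- **Few partial dates are likely near the switch.** Protocol Appendix A schedules AE and medication review at Weeks 50, 52, 53, 54 and 56. Protocol 8.5.3 requires a platelet value within 7 days before dosing and contact with the study doctor. SAP 2.5.1 describes checks that prompt for missing data. A year-only onset at this time is remote. This bears on size and leaves the direction unchanged.
- **No event is lost.** These AEs all follow the first dose, so treatment-emergent status holds. Listings show original dates, and an AE that worsens after the switch is counted in both periods.
- **The controlled comparison.** A reader might infer that the rule inflates placebo alone in the randomised-period table. The documents do not support that. The rule applies to both arms, so switch-month events of volanesorsen patients are also drawn into their randomised column. What differs is attribution: those patients are on volanesorsen on both sides of the switch, and placebo patients are not.
- **Medications in general.** A reader might infer that medications are pushed past the switch, opposite to AEs. That fails for a medication with a full stop date before the switch, whose start is reset to the stop date, and for year-only starts in a later switch year, which go to January 1 as AEs do. A medication spanning both periods is counted in both.
- **Bleeding analysis.** It is exploratory. Protocol exclusions 17i and 17l require stable use for at least 4 weeks before dosing, so established use normally starts before the first-dose month and stays linked. Only drugs newly started on study with an unknown day are affected, and some of those may truly have started after the bleed.

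**Conclusion.** The point holds for AE start dates in placebo patients who switch. In the switch month, SAP 3.7.1.1 assigns every day-missing AE to the placebo period unless the switch is on the 1st, although about half of the possible onset days follow the first volanesorsen dose. The direction is contrary to the principle that the section states. Only the analysis period is affected.

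The effect is probably small. The documents give neither the number of partial dates nor the number of placebo patients who switched, and SAP 3.8 says that treatment stopped before the planned period was complete. The half-month figure assumes switch days spread evenly within months. It would be wrong to read it as all such events being misplaced, since about 48% of the days are truly placebo days. The 80% for year-only dates describes a mid-March switch and is no general figure.

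The medication point holds only for a newly started antiplatelet or anticoagulant drug with an unknown start day and a bleed before its imputed start.

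**What to change.** In SAP 3.7.1.1, add one branch for placebo patients who enter the OLE: if a partial AE start is compatible with the month-year (or, for year-only dates, the year) of the first OLE dose, and the end date does not exclude it, impute the first OLE dose date. This mirrors the existing Day 1 branch. Leave the volanesorsen arm as it is; extending the branch to that arm would take events out of its randomised-period column.

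In SAP 3.7.2.3, for the bleeding analysis only, treat a day-missing medication start in the month of the bleed as on or before the bleed unless the recorded dates exclude it. Do not change the general rule in 3.7.1.2 to the first of the month. That would turn on-study starts in the first-dose month into prior medications under SAP 3.7.9, and would move some post-switch starts into the placebo period.

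The cost is two sentences and small derivation changes, with no new data. The downside is that some truly pre-switch placebo events move to the OLE period: about 48% of the days in the switch month, and 287/365 = 79% of the year for a year-only date with a 15 October switch. That is the conservative direction for drug safety. Because the branch depends on arm, it should be fixed before unblinding.
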